**PARTNERS HUMAN RESEARCH COMMITTEE
DETAILED PROTOCOL**

PRINCIPAL/OVERALL INVESTIGATOR

[name].

PROTOCOL TITLE

A Randomized Controlled Trial of an Advanced Care Planning Video Decision Support Tool for Patients with End-Stage Liver Disease (Clinicaltrials.gov Identifier NCT03557086)

FUNDING

NIH-NIDDK National Institute of Diabetes and Digestive and Kidney Diseases
4K24DK078772-10

VERSION DATE

Version 9: February 6, 2020

A Randomized Controlled Trial of an Advanced Care Planning Video Decision Support Tool for Patients with End-Stage Liver Disease

Version 9: February 6, 2020

SPECIFIC AIMS

The goal of this pilot randomized trial is to assess the feasibility and preliminary efficacy of an advanced care planning (ACP) video decision support tool for improving patients' knowledge regarding their goals of care options and end of life (EOL) decision-making in patients with end-stage liver disease (ESLD).

Aim 1: To assess the feasibility and acceptability of an ACP video decision support tool for patients with ESLD

- *Hypothesis 1: The intervention will be deemed feasible and acceptable if at least 60% of eligible patients are enrolled in the study and if at least 60% of patients randomly assigned to the video intervention report that the video is acceptable*

Aim 2: To assess the impact of an ACP video decision support tool on patients' knowledge about their EOL care options

- *Hypothesis 2: Patients randomly assigned to the video intervention will report improved knowledge of their EOL care options compared to those randomized to the verbal narrative control*

Aim 3: To assess the impact of an ACP video decision support tool on patients' preferences for EOL care

- *Hypothesis 3: Patients randomly assigned to the ACP video will be more likely to prefer comfort care compared to those randomized to the verbal narrative control arm*
- *Hypothesis 4: Patients randomly assigned to the video intervention will be more likely to forgo cardiopulmonary resuscitation (CPR) and intubation compared to those randomized to the verbal narrative control arm*

Aim 4: To assess the impact of an ACP video decision support tool on patients' documented EOL care preferences

- *Hypothesis 5: Patients randomly assigned to the video intervention will be more likely to have their code status documented in the electronic healthcare record compared to those randomized to the verbal narrative control arm*

BACKGROUND AND SIGNIFICANCE

End-stage liver disease (ESLD) is a terminal condition for which liver transplantation is the only cure. Heralded by the development of debilitating symptoms such as ascites, variceal bleeding, hepatic encephalopathy, or jaundice in patients with cirrhosis, ESLD is a state of limited life expectancy, with a median transplant-free survival of two years. Unfortunately, the diagnosis of ESLD is a terminal one for thousands of patients annually who are deemed ineligible for liver transplantation due to significant comorbid disease, substance use disorder, inadequate social support, or advanced age. However, despite their poor prognosis, patients with ESLD who are non-transplant candidates still receive aggressive medical care at the end of life (EOL). While most patients prefer to die at home, these patients are frequently hospitalized during the last month of A Randomized Controlled Trial of an Advanced Care Planning Video Decision Support Tool for Patients with End-Stage Liver Disease

life and have high rates of in-hospital mortality.¹⁻⁵ Furthermore, these patients often receive aggressive life-sustaining therapies during their terminal hospitalizations, such as cardiopulmonary resuscitation (CPR) and intubation.^{6,7} The Institute of Medicine report, *Dying in America*, highlighted substantial deficiencies in EOL care for patients with serious illness and identified intensive and costly care at the EOL as poor-quality care given its burden on patients, families, and the health care system.⁸ Thus, there is a critical need to optimize the quality of EOL care for patients with ESLD who are not transplant candidates given their terminal diagnosis, poor prognosis, and the frequency with which they receive intensive and costly medical care at EOL.

Advance care planning (ACP) is the process by which patients discuss their goals and preferences for medical care at the EOL with their clinicians.⁹⁻¹¹ Patients who engage in advance care planning are better informed about their EOL care options, which improves their EOL decision-making.¹²⁻¹⁸ Decisions about CPR and intubation are an integral part of advance care planning, and studies have shown that patients with life-limiting illnesses who discuss their EOL care preferences with their clinicians are less likely to opt for aggressive medical interventions.¹⁸⁻²³ Unfortunately, one retrospective analysis showed that only a minority (28%) of patients with ESLD ineligible for liver transplantation had documented advanced directives.⁷ Another series revealed that the majority of hospitalized patients with cirrhosis were designated full code on admission²⁴, despite multiple studies showing dismal outcomes after cardiac arrest for this population, with rates of survival ranging from 0% to 16%.²⁵⁻²⁹ Thus, interventions are needed to educate transplant-ineligible patients with ESLD of their care options at EOL in order enhance the frequency and quality of advance care planning for this vulnerable patient population.

Patients must receive accurate and understandable information about their medical options to make informed decisions about the care they would prefer to receive at the EOL.^{9,10} However, verbal communication strategies do not effectively inform patients of their EOL care options as they are often too complex for patients to comprehend.^{9-11,30-34} Patients frequently find it difficult to realistically envision care in the intensive care unit (ICU) or medical procedures such as CPR and intubation, especially given the variability in the quality of communication between patients and their clinicians.^{9-11,30-37} Videos can enhance patients' comprehension of complex health information by providing realistic visual images that can facilitate education about medical procedures, such as CPR and intubation.^{38,39} A video decision support tool offers an innovative strategy to educate transplant-ineligible patients with ESLD about CPR and intubation in order to empower them to make informed decisions regarding their EOL care.

RESEARCH DESIGN AND METHODS

Study Design and Schema:

Our proposed project is a single-center randomized controlled trial to assess the feasibility, acceptability and preliminary efficacy of an ACP video decision support tool versus a verbal narrative alone on EOL care preferences in transplant ineligible patients with ESLD in the outpatient setting. We will recruit up to 70 consecutive patients with ESLD who receive ambulatory care at the MGH Liver Center for this study. Patients will be randomized in a 1:1 fashion (**Figure 1**). To ensure that patients in this sample received longitudinal care (ruling out

A Randomized Controlled Trial of an Advanced Care Planning Video Decision Support Tool for Patients with End-Stage Liver Disease

Version 9: February 6, 2020

those being seen for second-opinion consultation), we will only include those patients who have had two or more visits to the MGH Liver Center.

Eligibility Criteria

Our proposed project is a single-center randomized controlled trial to assess the feasibility, acceptability and preliminary efficacy of an ACP video decision support tool versus a verbal narrative alone on EOL care preferences in transplant ineligible patients with ESLD. We will recruit up to 70 consecutive adult patients with ESLD who receive care at MGH for this study. Patients will be randomized in a 1:1 fashion (see **Schema for further details**).

Eligibility Criteria

All patients with ESLD who are \geq 18 years of age seen at the Massachusetts General Hospital will be screened for study participation. Our study population is defined as patients with cirrhosis complicated by at least one of the following clinically-evident decompensating events: 1) ascites; 2) hepatic encephalopathy; or 3) history of gastroesophageal variceal hemorrhage - which portends a poor prognosis.⁴⁰ Only patients who are deemed ineligible for liver transplantation by either their primary hepatologist or the inpatient hepatology consult service attending will be eligible for this study as this is a patient population for whom the diagnosis of ESLD is a terminal one.

Patients Inclusion Criteria:

[figure not shown]
1. \geq 18 years of age with an established diagnosis of ESLD
2. Patient must have either 1) primary hepatologist at the MGH Liver Center or an MGH-affiliated primary care physician, or 2) a previous inpatient admission at MGH
3. Deemed ineligible for liver transplantation as determined by the primary hepatologist or the inpatient hepatology consult service attending
4. Ability to communicate in English and provide informed consent
5. A score \geq 7 on the Short Portable Mental Status Questionnaire⁴¹ (**Appendix A**)

Patients Exclusion Criteria:

1. Severe hepatic encephalopathy which the primary hepatologist or the inpatient hepatology consult service attending believes prohibits informed consent or participation in the study
2. Significant uncontrolled psychiatric disorders (psychotic disorder, bipolar disorder, major depression) or other co-morbid disease (dementia, cognitive impairment), which the primary hepatologist believes prohibits informed consent or participation in the study
3. Prior history of liver transplantation
4. Patient has been referred to or enrolled in hospice care
5. Patient has been referred to palliative care

We have limited enrollment to patients able to comprehend English, as the video is only available in English at this time. If the intervention is effective in improving advance care planning and the delivery of EOL care for patients with ESLD, we will develop videos in additional languages for future trials.

Figure 1

Once a potentially eligible patient is identified, the RA will send an email to the primary hepatologist in the outpatient setting, or the medicine attending and responding clinician in the inpatient setting (as well as the hepatology consult service if available) to notify them that their patient is eligible for study participation and inquire about any concerns regarding their participation. If the clinicians have objections to their patients' participation in the study, we will document the reason and not approach those individuals. If the clinicians do not have objections to their patients' participation in the study, we will ask the attendings to introduce the study to the eligible patient to obtain permission for the study staff to approach the patient. After obtaining permission from the primary hepatologist, inpatient hepatology consult attending and/or medicine attending, the RA will review the consent form with potential participants which will detail the nature of the study procedures. When obtaining informed consent, the RA will describe the goal

A Randomized Controlled Trial of an Advanced Care Planning Video Decision Support Tool for Patients with End-Stage Liver Disease

Version 9: February 6, 2020

of the study: to better understand how much patients with ESLD know about ACP and EOL care preferences. The RA will also explain that the study requires completing a 15-minute baseline questionnaire asking participants about their CPR and intubation preferences, eliciting prior advance care planning discussions, and assessing their knowledge regarding CPR and intubation. The RA will undergo standardized training in all aspects of the research protocol, including the use of structured scripts to administer the questionnaires (**Appendix A**). For patients agreeing to participate in the study, the RA will obtain written informed consent from the participants and provide them with a copy of the signed consent form.

After obtaining informed consent, the RA will administer the Short Portal Mental Status Questionnaire (**Appendix B**) to participants to confirm final eligibility. Immediately following enrollment, the RA will administer a 15-minute baseline questionnaire (see “Study Measures” below) that will include the following: demographics, self-reported health status, baseline EOL care preferences, CPR and intubation preferences, and a questionnaire assessing patients’ knowledge of EOL care options.

Randomization

After enrollment and completion of the baseline questionnaires, participants will be randomized in 1:1 fashion without any stratification to either the control group (verbal narrative alone) or the intervention group (video decision support tool) using a random computer generated list, with assignments concealed in numbered envelopes.

The Intervention Arm

Our group, the VIDEO Consortium (Video Images of Disease for Ethical Outcomes), has developed several video decision support tools to assist patients with advance care planning.^{38,39,44} We have previously developed a five-minute advance care planning video for patients with advanced cancer⁴⁵, which has been adapted for this study.

We convened a panel of clinicians with expertise in hepatology, critical care, palliative care, medical ethics, and decision-making at our institution to develop a verbal narrative introducing the patient to advance care planning, a 3-part goals of care framework (life-prolonging care, limited medical care, and comfort care), and a description of medical procedures such as CPR and intubation that will outline the process, risks, and likelihood of successful resuscitation in patients with ESLD. This panel drafted and edit this narrative in an iterative process, which serves as the verbal script for our video decision support tool and the verbal narrative for our control group (**Appendix C**). These experts also offered feedback about the representation of medical interventions, such as what care in the ICU is like and what CPR and intubation look like.

We designed the video to provide non-medical trained individuals a general understanding of the types of medical care patients may receive at the EOL and a description of medical interventions such as hospitalizations, ICU admission, CPR, and intubation. The video begins by addressing the importance of the patient’s personal goals and perspectives by asking the viewer to reflect on their concerns about getting sick and their overall goals for their EOL care. The physician narrator then

introduces a framework for choices of medical care at the EOL including: 1) life-prolonging care; 2) limited medical care; and 3) comfort care. The visual images illustrating life-prolonging care include interventions that are available in a modern-day hospital such as CPR, mechanical ventilation, and treatment in the ICU. Scenes include an ICU with a ventilated patient being tended to by respiratory therapists, a simulated code conducted with clinicians illustrating chest compressions, CPR and intubation, and the administration of medications through a central venous catheter. For the second option, limited medical care, the narrator explains the goal of care is to pursue treatment for medical conditions, but avoid intensive medical interventions at the EOL. This type of care would include hospital care, intravenous medications, and antibiotics, but not CPR or ICU care. Visual images include a patient getting medicine via a peripheral venous catheter, scenes from a typical medical ward, and a patient wearing a nasal cannula to receive oxygen and breathing treatments. For the third option, comfort care, the narrator describes the goal of care as relieving symptoms and utilizing medical care that would only be used to provide comfort. Visual images include a patient on hospice care at home receiving pain medications, a patient with a respiratory face mask receiving oxygen at home, and an attendant assisting a patient with self-care. All three sequences of video images accompanying the narration attempt to help the viewer imagine the experience and likely outcomes of receiving these medical interventions at the EOL. The video was filmed and edited by the research team without the use of prompts or stage directions to convey a candid realism in the style known as *cinema vérité*. All patients included in the video (or their proxies) gave consent to be filmed.

Immediately after completing the baseline assessment and randomization, patients assigned to the video intervention arm will view the 3-minute advance care planning video for patients with ESLD on an iPad in the presence of the RA. We will use standardized procedures to minimize the interaction between the RA and patient while the patient is viewing the video. The RA will not be permitted to comment or answer questions while the patient views the video. Patients will be instructed to watch the video once without any interruption and will have no further exposure to the video. If patients have questions about the video or their EOL care options, the RA will instruct them to discuss their questions with their medical team.

The finalized video can be viewed by the IRB at the following link:

<https://vimeo.com/269740750>

Access Code: mghirb

The Control Arm

Immediately after completing the baseline assessment and randomization, patients assigned to the verbal narrative control arm will listen to the same description of the 3 goals of care used in the video arm read out loud by the RA (**Appendix C**). We will use standardized procedures to minimize interaction between the RA and patients during the interview. Specifically, the RA will not be permitted to comment or answer questions while the patients listen to the verbal narrative. Patients will be instructed to ask their physicians any questions they may have about goals of care.

Study Measures

A Randomized Controlled Trial of an Advanced Care Planning Video Decision Support Tool for Patients with End-Stage Liver Disease

Version 9: February 6, 2020

We will administer the following study measures at baseline prior to randomization, and immediately after the video or verbal narrative in the intervention and control group, respectively according to the timeline displayed in **Table 1**:

- *Demographics*: Patients will complete a demographic questionnaire at baseline detailing their age, sex, race/ethnicity, religion, relationship status, educational level, living situation, employment status, and self-reported health status (“Relatively healthy”, “Relatively healthy and terminally ill”, “Seriously ill and not terminally ill”, “Seriously ill and terminally ill”)⁴⁶ (**Appendix D**)
- *EOL Care Preferences*: Patients will report their EOL care preferences as follows: life-prolonging care, limited medical care, comfort care, or unsure. (**Appendix E**)
- *CPR Preferences*: Patients will report their CPR preferences as follows: “Yes, attempt CPR”, “No, do not attempt CPR”, or “Not sure.” (**Appendix E**)
- *Intubation Preferences*: Patients will report their intubation preferences as follows: “Yes, attempt intubation”, “No, do not attempt intubation”, or “Not sure.” (**Appendix E**)
- *Knowledge Questionnaire*: We will assess patients’ knowledge of goals of care as in previous studies using 5 true/false questions and 1 multiple choice question, each worth 1 point, for a summary score of 0 to 6 (higher score reflects greater knowledge)^{45,47,48} (**Appendix F**)
- *Acceptability of the Video*: For the video intervention arm alone, we will administer 3-items assessing patients’ comfort with watching the video, whether they find the video helpful in their understanding of the EOL care options, and whether they would recommend it to others.⁴⁹ (**Appendix G**)

We will also obtain the following important covariates and outcomes:

- *Disease-related variables*: We will collect variables from the EHR at the time of enrollment, including the etiology of ESLD, presence of clinically-evident decompensating events (ascites, esophageal variceal bleed, hepatic encephalopathy, or multiple), Model of End-Stage Liver Disease Sodium (MELD-Na) score, reason for transplant ineligibility, and clinical comorbidities using the modified Charlson Comorbidity Index.⁵⁰
- *Code Status Documentation in the EMR*: The RA will review the EHR to collect whether clinicians’ documented patients’ code status in the EMR (yes: documented, no: not documented) 3 months after study enrollment.

Table 1: Data Collection Timeline

	Baseline	Post-intervention	3 months post-enrollment
Demographics	X		
Self-Reported Health Status	X		
EOL Care Preferences	X	X	
CPR Preferences	X	X	
Intubation Preferences	X	X	

Knowledge Questionnaire	X	X	
Comfort/Satisfaction with Video (Intervention group only)		X	
Disease-related variables	X		
Code status documentation			X

We will collect and enter all patient data electronically using Research Electronic Data Capture (REDCap). The REDCap Survey is a tool for building and managing online surveys. Vanderbilt University, in collaboration with a consortium of institutional partners, has developed this software and workflow methodology for electronic collection and management of research and clinical trial data. Our research team has extensive experience using REDCap and will create and design the surveys in a web browser, with institutional information technology support. The REDCap Survey system offers secure, HIPAA compliant, web-based applications that provide an intuitive interface for participants to enter data, with real-time validation rules at the time of entry.

Participants will use tablet computers to complete questionnaires in clinic. If any participants refuse or are unable to complete the questionnaires on the computer, they will be permitted to use hard-copy paper versions. In addition, the patient data collected from the electronic health record will be abstracted throughout the study and directly inputted into REDCap.

Study Outcomes

- **Primary Outcome:** The primary outcome is feasibility. The proposed video intervention will be deemed feasible if at least 60% of eligible patients are enrolled in the study. The 60% feasibility cut-off is commonly used in behavioral intervention studies.⁵¹⁻⁵³
- **Secondary Outcomes:** The secondary outcomes will include patients' comfort/satisfaction with the video, patients' stated post-intervention EOL care preferences categorized as four options: Life-prolonging care, limited medical care, comfort care, or unsure; individual preferences for CPR and intubation before and after intervention in the verbal narrative and video groups; and change in knowledge scores after receiving the verbal narrative or video

Sample Size Calculation

We will randomize up to 70 patients with ESLD for this project. The primary endpoint of the study is feasibility. We chose the sample size of 70 patients based on the feasibility of completing the project during the proposed timeframe and the ability to assess the preliminary efficacy of the intervention. Consistent with the behavioral intervention literature, at least 20 patients are needed in each group in a pilot study to estimate a parameter.^{54,55} Therefore, the proposed sample size will provide us with preliminary data that can be utilized to determine the effect size and adequately power future randomized trials. This is a commonly utilized study design for pilot testing of behavioral interventions and is consistent with the National Institute of Health Stage Model for Intervention Development. While the feasibility of the intervention can be assessed using a single-arm design, preliminary efficacy is better assessed utilizing a control group as we are proposing in this trial.

A Randomized Controlled Trial of an Advanced Care Planning Video Decision Support Tool for Patients with End-Stage Liver Disease

Analysis Plan

We will report baseline demographic and clinical characteristics of all study participants using means and proportions to describe continuous and categorical variables, respectively. Because this is a pilot study, we will use conservative ($\alpha = 0.05$) and liberal ($\alpha = 0.20$) critical values to assess statistical significance between the two arms in this pilot study.

Aim 1: The primary endpoint of the proposed study is feasibility. The proposed video intervention will be deemed feasible if at least 60% (95% CI +/- 13.6%) of eligible patients are enrolled in the study and complete at least 60% of the intervention sessions. The proposed video intervention will be deemed acceptable if at least 75% of patients randomized to the intervention arm report satisfaction and comfort with the video.

Aim 2: Changes in knowledge scores from before and after the intervention will be compared between the two groups using two-sample t-tests.

Aim 3: Post-intervention EOL care preferences (life-prolonging care, limited medical care, and comfort care), CPR preferences, and intubation preferences will be compared between the two groups using Fisher's exact tests. The change in CPR and intubation preferences before and after the intervention within each group will be compared using McNemar tests.

Aim 4: Code status documentation will be compared between the two groups using Fisher's exact tests.

Project Timeline	Table 1: Study Timeline and Study Procedures
Months 0-2	❖ Finalize protocol development and submit to Institutional Review Board for approval
Months 3-24	Data Collection ❖ Enroll up to 70 patients to participate in the prospective study ❖ Collect follow-up data on ACP documentation and prepare manuscript(s) for publication

REFERENCES

A Randomized Controlled Trial of an Advanced Care Planning Video Decision Support Tool for Patients with End-Stage Liver Disease

Version 9: February 6, 2020

8. Dying in America: improving quality and honoring individual preferences near the end of life. *Mil Med*. 2015;180(4):365-367.
10. Gillick MR. Advance care planning. *The New England journal of medicine*. 2004;350(1):7-8.

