APPENDIX A: Script for Administering the Educational Methods

Introduction

Research staff member: My name is (state name) and I am a working on a project about what people prefer when receiving medical care at the end of life. The goal of this project is to understand what people think and what they like better when getting medical care for advanced liver disease. You are being asked to take part in this study because you have advanced liver disease. Taking part in the project is strictly up to you. You can decide to not answer any of the questions if you wish, and can stop the interview at any time. You may also see an educational video during this survey, and you can stop the video at any time. Taking part in this project will have no bearing on your current care. This interview will last about a half hour. Does this sound like a project you would like to participate in?

If YES: Research staff member will obtain written consent and administer the Short Portable Mental Status Questionnaire

If NO: Research staff member thank the patient and end the interview

Screening: Short Portable Mental Status Questionnaire (Appendix B)

Research staff member: First, I will ask you some general questions.

Administer Appendix B

If score is ≤ 6 : Research staff member thank the patient and end the interview

If score is 7 or higher: Research staff member will continue to baseline questionnaires

Baseline Questionnaires (Appendices D, E, and F)

Here are some questionnaires to fill out on your own, which will help us to learn more about how people with advanced liver disease feel and what they like better when getting medical treatment. Please ask the interviewer if you need help at any time

Study Randomization - If randomized to VIDEO

Research staff member: I will now play an educational video tool about the different medical care options for patients with advanced liver disease. I will not be able to answer any questions about the content of the video. However, you should feel free to bring up any questions that you have about choices for medical care for patients with advanced liver disease to your care team. Do you have any questions about the study procedures before we begin?

If YES: Research staff member will address questions

If NO: Research staff member will play the educational video tool

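### The Aim 4 code-status outcome is abstracted by the role that delivers the intervention, with no masking requirement and no fixed search rule, so search effort could differ by arm

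*Combined protocol and SAP*

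**What the plan says.** Under Study Measures, the item on code status documentation reads "The RA will review the EHR to collect whether" clinicians recorded it, and the result is "code status in the EMR (yes: documented, no: not documented) 3 months after study enrollment". Table 1 (Data Collection Timeline) lists this as the only item collected at 3 months.

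The RA role also delivers both arms. The Intervention Arm section has patients watch the video "on an iPad in the presence of the RA", and the Appendix A script states "Research staff member will play the educational video tool". The Control Arm section has the narrative "read out loud by the RA".

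On handling of chart data, the text after Table 1 says that "the patient data collected from the electronic health record will be abstracted throughout the study and directly inputted into REDCap". Under Randomization, allocation uses a computer-generated list "with assignments concealed in numbered envelopes".

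The Analysis Plan compares code status between arms with Fisher's exact test and uses critical values of 0.05 and 0.20. Hypothesis 5 expects more documentation in the video arm.

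**The concern.** The outcome depends on how the chart is searched, and its two answers are not symmetric. One entry found anywhere settles a yes. A no means only that the search stopped without a hit, so it depends on how many places were opened. The plan names no field, order, note type or encounter type. It also leaves open whether 3 months is the latest date of an entry that counts or only the date of the review.

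An abstractor who knows the arm and the expected direction could, without intending to, search longer in one arm. The envelopes do not guard against this, because they protect the assignment only until it is opened.

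At stake is the one outcome that reaches beyond the study session and the only measure of Hypothesis 5. The Sample Size Calculation section says the pilot data will be used to derive effect sizes for later trials, so a detection artefact would carry forward whatever the p-value.

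**Working it through.** **Text check.** Every mention of standardisation, masking or chart handling was set against the Aim 4 outcome.
- General RA training with questionnaire scripts (text before Randomization): not an abstraction rule.
- Limits on RA-patient interaction (both arm sections): these concern the session, not the chart.
- Concealed envelopes (Randomization): these act before allocation only.
- Direct entry into REDCap: no masking, second reader or named source.

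The gap is therefore in the text itself.

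**The plan's own figure.** There is none to reproduce: the plan gives no rate, effect size or power for Aim 4.

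**Illustration of size.** Inputs:
- From the plan: up to 70 patients, 1:1, hence n = 35 per arm if full and equal; Fisher's exact test; alpha 0.05 and 0.20.
- Assumed: a two-sided test (sidedness is not stated); a true documentation rate p that is the same in both arms; detection probabilities s_V (video) and s_N (narrative). The documents give no code-status rate. The 28% in the background refers to advance directives.

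Method:
- Recorded yes-counts are X_V ~ Bin(35, p·s_V) and X_N ~ Bin(35, p·s_N), independent.
- Spurious difference = p·(s_V − s_N).
- False favourable rate = sum of P(X_V = a)·P(X_N = b) over all a > b with two-sided Fisher p-value ≤ alpha.
- Total rejection is the same sum over both directions.

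Results for p = 40%:

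| Detection, video v narrative | Recorded rates | Spurious difference | Favours video, 0.05 / 0.20 | Total rejection, 0.05 / 0.20 |
|---|---|---|---|---|
| 95% v 95% | 38% v 38% | 0 points | 1.4% / 6.0% | 2.9% / 12.0% |
| 95% v 85% | 38% v 34% | 4 points | 3.3% / 11.6% | 3.9% / 14.5% |
| 95% v 80% | 38% v 32% | 6 points | 4.9% / 15.6% | 5.2% / 17.5% |
| 95% v 75% | 38% v 30% | 8 points | 7.0% / 20.4% | 7.2% / 21.7% |
| 95% v 70% | 38% v 28% | 10 points | 9.7% / 26.3% | 9.8% / 27.0% |

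Worked example of the difference: 0.40 × (0.95 − 0.80) = 0.06.

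**Sensitivity to p.** For 95% v 80% and p from 30% to 60%, the favourable rate runs from 3.6% to 6.7% at 0.05 and from 13.8% to 21.1% at 0.20. For 95% v 75%, total rejection at p = 28%, 50% and 70% is 4.9%, 8.5% and 15.6% at 0.05, and 18.1%, 24.5% and 36.0% at 0.20. The effect grows with the true rate.

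**Reading.** In a nominal two-sided test the favourable tail is 2.5% or 10%. Fisher's test is conservative here, so with equal search it sits well below those levels, and a gap of 10 points moves it only slightly above them. At p = 40%, total rejection passes both nominal levels from a gap of about 20 points. The table shows the direction that favours the video; more search in the narrative arm would hide a real effect in the same way.

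**The case against.** Several objections have force.

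- **The documents name a role, not a person.** A reader might infer that the abstractor knows the arm. The text does not establish that: a different RA could review the chart, 3 months after a single session. What stands is that nothing requires this or masks whoever does it.
- **The consequence depends on assumptions.** A reader might infer that a modest difference in search effort yields an apparent video effect. The figures do not bear that out. At 95% v 80% detection and 40% documentation, about 95% of trials still give no favourable result at 0.05, and total rejection (5.2% and 17.5%) is about at or below nominal. Nothing in the documents suggests that an RA would miss 20% to 30% of entries in one arm and 5% in the other.
- **The item is simple and the RA is trained.** It records whether an entry exists and does not rate its content, and training is said to cover all of the protocol. That limits discretion, but it does not say where to look or when to stop.
- **The stakes are limited.** Feasibility is primary, and code status is not among the secondary outcomes under Study Outcomes. That is correct. It caps the importance of the point without removing it, because Aim 4 has its own hypothesis and test.

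**Conclusion.** The concern holds as a risk that the plan leaves open, not as a demonstrated bias. The delivering role also abstracts the Aim 4 outcome, and neither masking nor a search rule is specified, so unequal search by arm could bias the only measure of Hypothesis 5.

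Its size is unknown. Under the assumptions above (35 per arm, 40% true documentation, two-sided test, no true effect), a detection gap of 10 to 15 points puts the false favourable rate at 3.3% to 4.9% at alpha 0.05 and 11.6% to 15.6% at 0.20, against 1.4% and 6.0% with equal search. A marked distortion of the test needs a gap of 20 points or more, somewhat less if documentation is more common than 40%. The estimate itself shifts with any gap: by 4 to 10 points in the cases tabulated for p = 40%.

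The feasibility conclusion is unaffected. The change is worth making because it is cheap and protects an effect estimate meant for planning later trials.

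**What to change.** In Study Measures, replace the open RA review with a prespecified rule:

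- Name the record locations that count: a structured code-status field if the record has one (the documents do not mention one), plus a fixed term search of notes.
- State the date window for entries that count, and use the same window for every patient.
- Apply the rule to all randomised patients from a list with no arm column, and merge arm only at analysis.
- Where a search hit has to be read, have it read without arm information and, where existing staffing allows, by a team member who did not deliver that patient's session.

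The cost is a few sentences of protocol text and a little set-up work. Visits, sample size and clinical procedures do not change.

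The rule has limits. Entries outside the named locations are missed. The same rule applies in both arms, but equal misses are not guaranteed, because clinicians might record in different places by arm. An RA who delivered a session may still recognise a patient, so masking may be incomplete.
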